2. STUDY OBJECTIVES AND ENDPOINTS

| OBJECTIVES | VARIABLES | ENDPOINTS |
|--|---|--|
| 
Primary study objective:
 
To investigate the efficacy of velusetrag in improving the symptoms severity associated with CIPO, in subjects with idiopathic CIPO and CIPO secondary to neurodegenerative or demyelinating conditions (e.g., Parkinsonian Syndromes, multiple sclerosis etc.).
 | 
Rating of each symptom (i.e., abdominal pain, bloating, nausea and vomiting) using a Likert scale from 0=Absent to 4=Extremely severe (precluding daily activities).
 | 
Primary study endpoint:
 
Change in weekly global gastrointestinal symptoms average index score* from pre-treatment to the end of each treatment period.
 
*The weekly global gastrointestinal symptoms average index score is obtained by averaging the scores for each of the 4 symptoms assessed weekly: abdominal pain, bloating, nausea and vomiting.
 
Rating of symptoms (i.e. abdominal pain, bloating, nausea and vomiting) is using a recall period of 7 days and a Likert scale with the following categories:
 
0 – Absent
 
1 - Mild (not influencing usual activities)
 
2 - Moderate (diverting from, but not urging modification of, usual activities)
 
3 - Severe (influencing usual activities markedly enough to urge modifications)
 |

[figure not shown]
| | |
|---|--|
|  | Statistical Analysis Plan |
| | Sponsor: Alfasigma S.p.A. Protocol: VE-CIP2001/2021 |

| OBJECTIVES | VARIABLES | ENDPOINTS |
|------------|-----------|---|
| | | 4 - Extremely severe (precluding daily activities) |

[figure not shown]

| | |
|---|--|
|  | Statistical Analysis Plan |
| | Sponsor: Alfasigma S.p.A. Protocol: VE-CIP2001/2021 |

[figure not shown]
| OBJECTIVES | VARIABLES | ENDPOINTS |
|------------|-----------|-----------|
|------------|-----------|-----------|

| | | |
|---|--|--|
|  | | |
|---|--|--|

[figure not shown]
| | |
|---|--|
|  | Statistical Analysis Plan |
| | Sponsor: Alfasigma S.p.A. Protocol: VE-CIP2001/2021 |

| OBJECTIVES | VARIABLES | ENDPOINTS |
|---|-----------|-----------|
|  | | |

| | |
|---|--|
|  | Statistical Analysis Plan |
| | Sponsor: Alfasigma S.p.A. Protocol: VE-CIP2001/2021 |

| OBJECTIVES | VARIABLES | ENDPOINTS |
|---|-----------|-----------|
|  | | |

| | |
|---|--|
|  | Statistical Analysis Plan |
| | Sponsor: Alfasigma S.p.A. Protocol: VE-CIP2001/2021 |

| OBJECTIVES | VARIABLES | ENDPOINTS |
|--|-----------|-----------|
|  | | |

3. BACKGROUND AND RATIONALE

[figure not shown]
3.1. Overall Study Design and Plan Description

This is a phase II, multicenter, double-blind, placebo-controlled, two-treatment four-period cross-over, multiple (n=1) trial to evaluate the efficacy and safety of velusetrag 15 mg once a day, compared to placebo, in subjects with a diagnosis of idiopathic CIPO or CIPO secondary to primary neurodegenerative or demyelinating conditions (e.g., Parkinsonian Syndromes, multiple sclerosis, etc.).

Eligible subjects will be treated for 4 periods of 4 weeks each with either velusetrag 15 mg (2 periods) or placebo (2 periods), once daily, with a wash-out period of 2 weeks between treatment periods. The scheme of study design is provided in Figure 1 below.

Figure 1: Schematic study design

| | |
|--|---|
| | <h2>Statistical Analysis Plan</h2> |
| | 
Sponsor: Alfasigma S.p.A.
 
Protocol: VE-CIP2001/2021
 |

After an up to 7-day screening period (from Day -7 to Day -1, V1), at randomization visit (V2), eligible subjects will be randomly allocated to one of the following four sequences:

- A. VEL-PLA-VEL-PLA
- B. PLA-VEL-PLA-VEL
- C. VEL-PLA-PLA-VEL
- D. PLA-VEL-VEL-PLA

Where:

VEL= velusetrag 15 mg once daily for 4 weeks.
 PLA= matching placebo once daily for 4 weeks.

[figure not shown]
There will be a 2-week wash-out period between each treatment period and a final 2-week follow-up period at the end of the last treatment period.

Subjects will be assessed during a total of 10 visits during the study, as detailed in the Study Schedule of Assessments, including the screening visit, a start of treatment visit (SOT) and an end of treatment visit (EOT) for each of the 4 treatment periods, for a total of 8 visits, and a final End of Follow up Visit (EFU), 2 weeks after the end of the last treatment period.

If the subject cannot go back to the clinical center for one or more of the following visits: EOT- 2 (Visit 5), EOT- 3 (Visit 7), EOT- 4 (Visit 9), End Of Follow Up (EFU, Visit 10) or in case of an early termination visit (ETV), the visit will be scheduled at the subject’s home and will be performed by a home nursing service. The clinical study staff at the clinical center may also attend the visit remotely.

| | |
|---|--|
|  | Statistical Analysis Plan |
| | Sponsor: Alfasigma S.p.A. Protocol: VE-CIP2001/2021 |

Overall, each subject will be involved in the study for a screening period of up to 7 days before randomization and approximately a 24-week period after randomization.

[figure not shown]
Subjects under treatment with a 
 must have a 5-day wash-out period before randomization (note: symptomatic treatments other than  will be permitted throughout the study, see section 10.8 Prior and Concomitant Therapy in the study protocol).

If, during a treatment period or during a wash-out period, a subject should experience an exacerbation of CIPO related gastrointestinal symptoms that is not controlled by permitted medications and is not judged as an adverse event, he/she will attend an early switch visit (ESV) at the clinical site. After being reassessed, he/she will be offered to directly switch to the next scheduled treatment period (SOT-2 or SOT-3 or SOT-4) without completing the ongoing treatment or wash-out period. Only one early switch is possible during the study. ESV will be Day 1 of the relevant period (SOT-2 or SOT-3 or SOT-4) based on the timing of early switch.

In case of ESV/SOT-2 or ESV/SOT-3 or ESV/SOT-4, the subsequent visits will follow the relevant sequential number (see Study Schedule of Assessments in section 3.4).

3.2. Selection of Study Population

Sixteen male and female subjects with a diagnosis of idiopathic CIPO or CIPO secondary to primary neurodegenerative or demyelinating conditions (e.g., Parkinsonian Syndromes, multiple sclerosis, etc.) who meet all the inclusion and none of the exclusion criteria will be enrolled in this study.

Subjects will be enrolled in up to 5 centres.

A complete list of all inclusion criteria and exclusion criteria are provided in Section 9.2 and 9.3 of the study protocol, respectively.

| | |
|--|--|
| | Statistical Analysis Plan |
| | Sponsor: Alfasigma S.p.A. Protocol: VE-CIP2001/2021 |

3.3. Treatment

3.3.1. Treatment Administered

The investigational products that will be administered in the study were:

- Velusetrag

[REDACTED]

- Placebo

[REDACTED]

3.3.2. Method of Assigning Subjects to Treatment Group

Eligible subjects will be randomly allocated in a 1:1:1:1 manner (4 subjects per treatment sequence), in a blinded fashion, to one of the following four treatment sequences:

- VEL-PLA-VEL-PLA
- PLA-VEL-PLA-VEL
- VEL-PLA-PLA-VEL
- PLA-VEL-VEL-PLA

Where:

VEL= velusetrag 15 mg ([REDACTED] mg [REDACTED]) once a day for 4 weeks.

PLA= matching placebo ([REDACTED]) once a day for 4 weeks.

[figure not shown]
Since the study is a cross-over study, each subject will take both investigational products during the study according to treatment sequence assigned by randomization.

Randomization will be stratified into 3 strata by CIPO diagnosis (idiopathic or secondary to neurodegenerative or demyelinating disease) and by [REDACTED] responder status (responder/naive or non-responder) as follows:

- [REDACTED] non-responder
- [REDACTED] responder/naïve and idiopathic CIPO

[figure not shown]
| | |
|---|--|
|  | Statistical Analysis Plan |
| | Sponsor: Alfasigma S.p.A. Protocol: VE-CIP2001/2021 |

-    responder/naïve and CIPO secondary to neurodegenerative or demyelinating disease.

Non responders are defined as all subjects that, based on investigator's judgement, have an history of a lack of benefit 

3.3.3. Prior and Concomitant Therapy

Use of the following medications is not allowed within 2 weeks prior to Screening and/or planned throughout the duration of the study:

- Scopolamine 
- Erythromycin 
- Strong CYP3A4 inhibitors or strong CYP3A4 inducers.

| | |
|--|---|
|  | |
|  |   |
|  |  |
|  |  |
|   |  |
|  |  |
|   |  |
|  |  |
|   |  |
|  |  |
|  |  |
|  | |
|  |  |

| | |
|---|--|
|  | Statistical Analysis Plan |
| | Sponsor: Alfasigma S.p.A. Protocol: VE-CIP2001/2021 |

| | (not exhaustive list*) |
|---|---|
|  |  |
|  |  |
|  |  |
|  |  |
|  |  |
|  |  |
|  |  |

- Strong P-gp transporter inhibitors.

| Strong P-gp Inhibitors | |
|---|---|
|  |  (not exhaustive list*) |
|  |  |
|  |  |
|  |  |
|  | |
|  |  |
|  | |
|  |  |
|  |  |
|  |  |
|  | |
|  |  |
|  |  |
|  |  |
|  |  |
|  |  |
|  |  |
|  |  |

| | |
|--|---|
| | Statistical Analysis Plan |
| | 
Sponsor: Alfasigma S.p.A.
 
Protocol: VE-CIP2001/2021
 |

| | |
|--|--|
| | |
| | |
| | |
| | |

- Strong BCRP transporter inhibitors.

| | |
|--|--|
| | |
| | |
| | |
| | |

In addition, use of:

- Opioids is not allowed within 8 weeks from screening and/or planned throughout the duration of the study. [REDACTED]
- [REDACTED] are not allowed starting from 5 days before randomization and throughout the duration of the study

| | |
|--|--|
| | |
| | |
| | |
| | |

*As the list of prohibited agents is not exhaustive, the selection of prohibited medications done by using ATC and PT will be confirmed through a medical review of all concomitant medications (including medications for CIPO)

Orally poorly absorbed opioids [REDACTED] that could be used to treat potential adverse events, such as diarrhea, may be used if medically indicated.

If a [REDACTED] or scopolamine, or erythromycin and an opioid for analgesic use is taken during the study, the subject will be considered a treatment failure and will be withdrawn from the study.

Additional prescription and over-the-counter medications are permitted, provided that such agents are not known to be strong inducers or inhibitors of CYP3A4, P-gp and BCRP activity.

| | |
|--|---|
| | Statistical Analysis Plan |
| | 
Sponsor: Alfasigma S.p.A.
 
Protocol: VE-CIP2001/2021
 |

The selection of prohibited medications will be done by using ATC and PT and it will be reviewed and confirmed through a medical review of all concomitant medications (including medications for CIPO).

Any addition or change in regimen of concomitant medications that affect CYP3A4, P-gp and BCRP activity should be in accordance with inclusion or exclusion criteria and recorded in the source documents and the electronic-case report form (eCRF).

Medication(s) used to relieve main symptoms of CIPO are allowed and the use of the following concomitant medications will be registered in the e-diary daily:

- Treatments for nausea and vomiting and/or non-serotonergic prokinetics.
- Treatments for constipation.
- Treatments for diarrhea.
- Treatments for abdominal pain.
- Others (e.g., octreotide, somatostatin, pancreatic enzymes, probiotics, rifaximin, metronidazole, fluconazole, etc.).

Further details on prohibited and permitted medications are reported in Section 10.8 PRIOR AND CONCOMITANT THERAPY of the study protocol.

3.4. Schedule of Time and Events

The schedule of assessments is shown in Table 3.4.1.

Table 3.4.1: STUDY SCHEDULE OF ASSESSMENTS

| | Screening Period | 1 st Treatment Period ^a | | 2 nd Treatment Period ^a | | 3 rd Treatment Period ^a | | 4 th Treatment Period ^a | | EFU ⁿ | ETV | ESV ^o |
|--|------------------|---|--------|---|--------|---|---------|---|---------|------------------|-------------------------|--------------------------------|
| | | Randomiz. SOT-1 | EOT-1 | SOT-2 | EOT-2 | SOT-3 | EOT-3 | SOT-4 | EOT-4 | End of Follow-up | Early Termination Visit | Early switch Visit |
| Visit | V1 | V2 | V3 | V4 | V5 | V6 | V7 | V8 | V9 | V10 | ETV | ESV |
| Day | -7 to -1 | 1 | 28(±1) | 43(±1) | 70(±1) | 85 (±1) | 112(±1) | 127(±1) | 154(±1) | 169(±1) | | Any time between Day 1 and 126 |
| Informed Consent | X | | | | | | | | | | | |
| On Site Visit | X | X | X | X | | X | | X | | | | X |
| On Site Visit or home visit ^b | | | | | X | | X | | X | X | X | |
| Medical, surgical history and previous medications | X | | | | | | | | | | | |

| | |
|--|------------------------------------|
| | <h2>Statistical Analysis Plan</h2> |
| Sponsor: Alfasigma S.p.A. Protocol: VE-CIP2001/2021 | |

| | Screening Period | 1 st Treatment Period ^a | | 2 nd Treatment Period ^a | | 3 rd Treatment Period ^a | | 4 th Treatment Period ^a | | EFU ⁿ | ETV | ESV ^o |
|--|------------------|---|-------|---|-------|---|-------|---|-------|------------------|-------------------------|--------------------|
| | | Randomiz. SOT-1 | EOT-1 | SOT-2 | EOT-2 | SOT-3 | EOT-3 | SOT-4 | EOT-4 | End of Follow-up | Early Termination Visit | Early switch Visit |
| Visit | V1 | V2 | V3 | V4 | V5 | V6 | V7 | V8 | V9 | V10 | ETV | ESV |
| Assessment of responder status | X | | | | | | | | | | | |
| Demographics | X | | | | | | | | | | | |
| [Redacted] | | | | | | | | | | | | |
| [Redacted] | | | | | | | | | | | | |
| [Redacted] | | | | | | | | | | | | |
| [Redacted] | | | | | | | | | | | | |
| [Redacted] | | | | | | | | | | | | |
| [Redacted] | | | | | | | | | | | | |
| [Redacted] | | | | | | | | | | | | |
| [Redacted] | | | | | | | | | | | | |
| [Redacted] | | | | | | | | | | | | |
| [Redacted] | | | | | | | | | | | | |
| [Redacted] | | | | | | | | | | | | |
| [Redacted] | | | | | | | | | | | | |
| [Redacted] | | | | | | | | | | | | |
| [Redacted] | | | | | | | | | | | | |
| [Redacted] | | | | | | | | | | | | |
| Inclusion/ Exclusion Criteria Evaluation | X | X | | | | | | | | | | |
| Randomization | | X | | | | | | | | | | |
| [Redacted] | | | | | | | | | | | | |
| [Redacted] | | | | | | | | | | | | |

| | |
|--|---|
| | Statistical Analysis Plan |
| | 
Sponsor: Alfasigma S.p.A.
 
Protocol: VE-CIP2001/2021
 |

- k. Dose to be taken under observation at each scheduled visit at the clinical center. The exact time of dose administration should be recorded at all visits.
- l. If the subject cannot go back to the clinical center for Visit 5, 7, 9 or ETV, the empty packs and the unused investigational product of the relevant period will be collected by the study nurse during the home visit.
- m. In all subjects on V2 and V3, blood samples will be collected [REDACTED]. Actual time of collection must be recorded for each sample.
- n. The final 2 week follow up period are considered also as final 2 week wash out period for the 4th treatment period.
- o. In case, during a treatment period or during a washout period, a subject should experience an exacerbation of the CIPO related gastrointestinal symptoms that is not controlled by permitted medications and is not judged as an adverse event, he/she will attend an early switch visit (ESV) at the site. After being reassessed, he/she will start the next scheduled treatment period (SOT-2 or SOT-3 or SOT-4), without completing the ongoing treatment or washout period. ESV will be Day 1 of the relevant period (SOT-2 or SOT-3 or SOT-4) based on the timing of early switch. Only one early switch is allowed during the study.

3.5. Sample Size and Power Estimation

The sample size is based on the main analysis (t-test) of the primary endpoint, which consists in the differences between velusetrag and placebo within each paired treatment cycle (2 per subject).

A total of 16 subjects [REDACTED] will be randomized leading to 32 pairs. Accounting for 25% dropouts/missing pairs, 18 pairs should be available for the primary analysis on the subgroup of subjects with history of benefit [REDACTED] or naïve [REDACTED] and 24 pairs should be available for the analysis on the overall population.

With a two-sided significance level of 5%, the planned sample size will lead to power levels above 80% to detect effect size (ES) above 0.7 (see table 3.5.1 below).

Table 3.5.1 Power for different values of effect size and number of pairs

| Power for different values of Effect Size* and number of pairs | | | |
|--|---------|---------|---------|
| Number of pairs | ES: 0.6 | ES: 0.7 | ES: 0.8 |
| 18 | 67% | 80% | 89% |
| 24 | 80% | 91% | 96% |
| 28 | 86% | 94% | 98% |
| 32 | 91% | 97% | 99% |

** More than medium to moderate effect size (Cohen, 1988)
Estimates obtained using SAS PROC POWER*

If based on a blinded review of the data the rate of missing pairs is found to be higher, the sample size might be increased by the Sponsor.

| | |
|---|--|
|  | Statistical Analysis Plan |
| | Sponsor: Alfasigma S.p.A. Protocol: VE-CIP2001/2021 |

4. DEFINITIONS AND GENERAL METHODOLOGY

4.1. General Methodology

Statistical tables, figures, listings and analyses will be produced using SAS® for Windows release 9.4 or later (SAS Institute Inc., Cary, NC, USA).

Data from all sites will be pooled and summarized. Continuous data will be summarized by the number of observations, mean, standard deviation (SD), median, first and third quartiles (i.e., 25th and 75th percentiles), minimum and maximum. Categorical data will be presented by absolute and relative frequencies (n and %).

All efficacy analyses have the objective to show the superiority of velusetrag over placebo. All statistical analysis will be two-sided at a nominal level of 5%. Confidence intervals will be set at the 95% level.

4.2. Definitions

Study Phases

Screening phase (i.e., Visit 1): the screening phase is defined as starting from the screening visit up to randomization.

The screening visit can be performed within Day -7 and Day -1 before randomization.

First treatment period running from Visit 2 to Visit 3 and corresponding to the first period in which subjects took the first treatment assigned at randomization according to treatment sequence.

Wash-out after first treatment period corresponds to the 2-weeks after Visit 3 (EOT-1) in which subjects will not take any investigational product.

Similarly, there will be a **second, third and fourth treatment period** running from each respective start of treatment visit (SOT-2, SOT-3 and SOT-4) to each end of treatment visit (EOT-2, EOT-3 and EOT-4) after 28 days.

Wash-out periods after second and third treatment period corresponds to the 2 weeks after EOT-2 and EOT-3 respectively. Finally, the **follow-up of 2-weeks** corresponds to the 2 weeks after the EOT-4. During these phases the subject will not take any investigational product.

[figure not shown]
Definition of cycles

Each subject will be followed for two cycles of both treatments (i.e., VEL-PLA or PLA-VEL). The 1st cycle is made up of Period 1 and Period 2. The 2nd cycle is made up of Period 3 and

| | |
|--|--|
| | Statistical Analysis Plan |
| | Sponsor: Alfasigma S.p.A. Protocol: VE-CIP2001/2021 |

Period 4. In the Figure 2 below there are represented period and cycle based on study design.

Figure 2: Schematic design of period and cycle

Definition of Screening Failures

A screening failure is defined as a subject who signs the informed consent and has not been randomized to treatment.

Definition of Baseline/Reference

Due to the cross-over study design structure, for efficacy evaluation Baseline (for Period 1)/Reference (for Period 2, 3, 4) values are the last values collected prior to each treatment period initiation. For eDiary data the Baseline/Reference values are those recorded at the day before the start of treatment visit (Day -1 for Period 1, end of wash-out for the Period 2, 3, 4), while for other variables recorded in eCRF the Baseline/Reference are the last values collected before each treatment period first intake.

The Baseline for changes computation for the safety assessments is at the Visit 2 (SOT-1) except for laboratory data that is Visit 1.

For efficacy evaluation after the discontinuation of each treatment, the reference for changes computation is defined as the end of treatment visit for each period: Visit 3 (EOT-1) for period 1, Visit 5 (EOT-2) for period 2, Visit 7 (EOT-3) for period 3 and Visit 9 (EOT-4) for period 4.

| | |
|---|--|
|  | Statistical Analysis Plan |
| | Sponsor: Alfasigma S.p.A. Protocol: VE-CIP2001/2021 |

In case of early switch visit or premature interruption of treatment, the reference for changes computation within each period should be adjusted accordingly based on ESV visits.

First/Last Administration of Study Treatment

Considering the overall study, the date of first administration of treatment (i.e., velusetrag or placebo) is the earliest start date of the 4 periods reported in the “Study treatment dispensed” CRF page while the date of last administration of treatment (i.e., velusetrag or placebo) is the date reported in the “End of treatment disposition” CRF page (i.e., maximum of the last administration of the 4 periods).

According to the study design, subjects will not receive the treatment during the wash out periods. For each study period, the date of first administration of treatment is the start date reported in the “Study treatment dispensed” CRF page on the corresponding SOT visit (i.e., Visit 2 (SOT-1) for period 1, Visit 4 (SOT-2) for period 2, Visit 6 (SOT-3) for period 3 and Visit 8 (SOT-4) for period 4) while the date of last administration of treatment is the last treatment intake date reported in the “Study treatment returned” CRF page on the corresponding EOT visit (i.e., Visit 3 (EOT-1) for period 1, Visit 5 (EOT-2) for period 2, Visit 7 (EOT-3) for period 3 and Visit 9 (EOT-4) for period 4). In case of early switch visit or premature interruption of treatment, the first and last intake within each period should be adjusted accordingly.

Study day

The study day describes the day of the event or assessment date relative to the reference start date, which is defined as the date of Randomization.

The study day will be calculated as the difference between the date of each considered efficacy/safety assessment and the reference start date plus 1 day.

If the considered event starts before the Randomization date, the study day will be calculated as the difference between the date of the assessment and the reference start date. Therefore, the study day will be negative.

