16.2.5 Disposition, Demographic and Other Baseline Variables

The number of subjects screened, failed screening (and reason for screening failure), randomized, treated and completing the study treatment periods (and reason for not completing) will be presented in frequency tables by treatment sequence and stratum.

The number of subjects in each analysis population (SS, FAS, mFAS1, and PPS) will be summarized by treatment sequence and stratum.

All major protocol violations will be presented as a frequency table by treatment sequence.

Baseline values are the last recorded values collected prior to treatment initiation.

Subject demographics, medical history and disease characteristics and others baseline characteristics measured before randomization will be summarized descriptively by treatment sequence on the FAS. Selected summaries will be done by treatment sequence and stratification factors (details to be provided prospectively in the SAP).

Selected baseline data will be also summarized on the mFAS1 and PPS.

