16.3 STATISTICAL AND ANALYTICAL PLANS

A detailed Statistical Analysis Plan (SAP) analysis plan will be developed and approved prior to unblinding.

Descriptive statistics per sequence, visit/period, and stratum will be presented as number of observations, number of missing observations, mean, standard deviation, median, minimum and maximum and 25th and 75th percentiles for continuous variables; frequency distribution (n, %) for categorical variables.

Graphical visualization for each subject overtime, including all assessments, will be used for the evaluation of efficacy and safety.

All efficacy analyses have the objective to show the superiority of velusetrag over placebo. All statistical analysis will be two-sided at a nominal level of 5%. Confidence intervals will be set at the 95% level.

Analysis of the primary efficacy endpoints will be performed on the mFAS1, FAS and PPS. Results on the mFAS1 will be considered primary. For secondary endpoints, analysis will be performed on selected populations. Details will be provided in the SAP.

Safety analysis based on SS will be presented by actual treatment received in each period.

Most recent version of appropriate coding dictionaries will be used.

SAS software (Version 9.3 or subsequent) will be used for all statistical analyses.

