6.4.3. Adverse Events

Treatment-emergent adverse events (TEAEs) will be reported by actual treatment. Adverse events starting on or after the first intake of treatment (i.e., first intake in the period 1) are considered TEAEs. 

| | |
|---|--|
|  | Statistical Analysis Plan |
| | Sponsor: Alfasigma S.p.A. Protocol: VE-CIP2001/2021 |

In addition, TEAEs will be summarized by actual treatment, MedDRA System Organ Class and Preferred Terms considering:

- 
- 

Adverse events will be classified as velusetrag emergent if the last treatment taken before the start of the adverse event was velusetrag, or placebo emergent if the last treatment taken before the start of the adverse event was placebo.

In addition, a summary of TEAEs will be provided by treatment sequence. 

[figure not shown]
- 
- 

[figure not shown]

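### Safety changes are taken from one baseline before Period 1 but shown by the treatment of each period, which dilutes the velusetrag–placebo contrast for any change that outlasts wash-out

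*SAP*

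**What the plan says.** - **Safety baseline (SAP 4.2).** "The Baseline for changes computation for the safety assessments is at the Visit 2 (SOT-1) except for laboratory data that is Visit 1". No readable sentence gives safety a reference for Periods 2 to 4.
- **Efficacy baseline (SAP 4.2, same definition).** "Due to the cross-over study design structure, for efficacy evaluation Baseline (for Period 1)/Reference (for Period 2, 3, 4) values are the last values" taken before each period starts. One endpoint in SAP 6.3.2, whose name is blacked out, follows the same logic: V4−V1, V6−V4, V8−V6 and V10−V8.
- **Protocol 16.2.5.** "Baseline values are the last recorded values collected prior to treatment initiation". It does not say whether this means the first treatment or each period's treatment.
- **Presentation (protocol 16.3).** "Safety analysis based on SS will be presented by actual treatment received in each period".
- **Adverse events (SAP 6.4.3).** "Adverse events will be classified as velusetrag emergent if the last treatment taken before the start of the adverse event was velusetrag", with the matching rule for placebo.
- **Design (SAP 3.3.2 and 3.1).** "Eligible subjects will be randomly allocated in a 1:1:1:1 manner (4 subjects per treatment sequence), in a blinded fashion", to VPVP, PVPV, VPPV or PVVP, "with a wash-out period of 2 weeks between treatment periods".

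The table layouts in SAP 6.4.4 to 6.4.6 are largely blacked out. Vital signs and biometrics (6.4.5) are described as descriptive, and no formal safety test is visible.

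**The concern.** Two rules pull apart. The value is credited to the treatment of the current period, but the change is counted from before Period 1. If something shifts on velusetrag in Period 1 and has not returned to its starting level, the following placebo period also shows a change from baseline. The same happens in reverse for a shift that starts on placebo. The SAP saw this problem for efficacy and reset the reference there, but did not do so for safety.

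Wash-out is not always completed either. Under the early-switch rule (protocol 6, SAP 3.1) a subject can go straight to the next treatment, so even a reversible change may still be present when that treatment begins.

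At stake is how well the objective safety data show which treatment a lasting change began on. There are 16 subjects and no data monitoring committee (protocol 9.1 and 18.4), so a few displaced values can shape a descriptive table.

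**Working it through.** No figure in the plan bears on this point, so there is none to reproduce. The check is an enumeration.

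**Inputs**
- Sequences A VPVP, B PVPV, C VPPV, D PVVP, equally allocated (SAP 3.1, 3.3.2).
- Single baseline before Period 1 (SAP 4.2); results credited to the period's treatment (protocol 16.3).
- Assumption, not in the documents: a change d is present at the end of every velusetrag period, a fraction r of it survives wash-out and stays to the end of the study, and placebo adds nothing. I vary r from 0 to 1.

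**Step 1. Count the exposed periods.** Placebo periods that come after a velusetrag period: A 2, B 1, C 2, D 1, so 6 of 8. Velusetrag periods with a later placebo period: A 2, B 1, C 1, D 2, again 6 of 8. Swapping the labels turns A into B and C into D, so the counts are the same for a change that begins on placebo.

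**Step 2. Single baseline, as written.** Velusetrag mean = d. Placebo mean = (6/8)·r·d = 0.75rd. Contrast = d(1 − 0.75r).

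**Step 3. Reference before each period.** A subject's first velusetrag period shows d and the second shows d − rd, so the velusetrag mean is d(1 − 0.5r). A placebo period starts and ends at the same level, so the placebo mean is 0. Contrast = d(1 − 0.5r).

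| r | Single baseline: velusetrag / placebo | Contrast | Period reference: contrast |
|---|---|---|---|
| 0 | 1.00d / 0 | 1.00d | 1.00d |
| 0.25 | 1.00d / 0.19d | 0.81d | 0.88d |
| 0.50 | 1.00d / 0.38d | 0.63d | 0.75d |
| 0.75 | 1.00d / 0.56d | 0.44d | 0.63d |
| 1 | 1.00d / 0.75d | 0.25d | 0.50d |

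**Step 4. By sequence, single baseline.** In A and C both placebo periods carry rd, so the contrast is d(1 − r), which is zero at r = 1. In B and D one of the two placebo periods carries rd, so the contrast is d(1 − 0.5r), the same as with a period reference. The average is [(1 − r) + (1 − 0.5r)]/2 = 1 − 0.75r, which agrees with Step 2. The whole shortfall against the period reference, 0.25rd on average, comes from the velusetrag-first sequences.

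**Step 5. A permanent yes/no abnormality.** Assume onset risks of 0.20 per velusetrag period and 0.05 per placebo period. The probability of still being normal is multiplied by 0.80 or 0.95 each period; in A it runs 0.80, 0.76, 0.608, 0.5776. Averaged over the four sequences:
- Single baseline (abnormal at period end): 31.4% of velusetrag periods v 24.8% of placebo periods, difference 6.6 points.
- Period reference (newly abnormal): 17.2% v 4.0%, difference 13.2 points.

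The ratio is 6.6/13.2 = 0.5. The difference was also halved for the other unequal risk pairs tried.

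**Step 6. Drift.** With a drift of one unit per period and no treatment effect, mean velusetrag minus mean placebo is −1 in A (2 − 3), +1 in B (3 − 2), and 0 in C and D (2.5 − 2.5). The average is 0.

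**The case against.** **The loss depends on persistence, and the documents lean against it.** Protocol 7 bases the wash-out on the half-lives of the drug and its active metabolite. Protocol 8 describes one signal seen on the first two days of dosing and not after six days. For effects of that kind r may be near zero and the two methods agree. This stands, although half-life governs clearance of the drug and does not show that every laboratory or weight change reverses within two weeks.

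**Other displays help to show onset.** Protocol 16.3 also asks for descriptive statistics by sequence and visit or period, and for individual plots over time covering efficacy and safety. With 16 subjects those plots would show much of what the by-treatment table obscures. Adverse events, which by the protocol 15.1.1 definition can include abnormal laboratory findings, are attributed by onset. This stands and limits the severity.

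**A single untreated baseline has merits.** It keeps cumulative harm visible, fits one reading of protocol 16.2.5, and drops out of a within-subject velusetrag–placebo difference. A period reference adds the error of each reference value and can hide a change already present: in VPVP a change persisting from Period 1 would show as zero in the second velusetrag period. This stands as a reason not to replace the single baseline.

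**Stronger readings that the documents do not support**
- A reader might infer that the safety contrast is cancelled. Even at full persistence 0.25d remains on average; it is zero only in A and C.
- A reader might infer that 6 of 8 means three quarters of lasting changes would be tabulated as one against one. That needs full persistence and a subject-level count by treatment, and no such table is readable.
- A reader might infer that, because the baseline is about 22 weeks old by Day 154 (153/7 ≈ 21.9), drift distorts the comparison. Each period has two sequences on each treatment, so under the planned allocation drift raises both columns alike.
- A reader might take the baseline to be a pre-study visit throughout. Only laboratory data use Visit 1; other safety data use Visit 2, the start of Period 1.

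**Conclusion.** The point holds as a minor one. The single safety baseline is in the text, it differs from the rule the SAP adopts for efficacy, and combined with presentation by period treatment it shows a persisting change under both treatments. The contrast is then d(1 − 0.75r) instead of d(1 − 0.5r): half as large at full persistence, slightly smaller at 25%, and unchanged when the change reverses in wash-out. A period reference does not recover the full d either.

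These sizes rest on the assumed persistence pattern, planned allocation and complete data. That the single baseline applies in every period is the natural reading of SAP 4.2, but the blacked-out layouts prevent confirmation. The conclusion covers laboratory values, vital signs and ECG-type measurements and does not extend to adverse events.

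**What to change.** Keep the change from V1/V2 as the display of cumulative effect. In SAP 4.2 and 6.4.4 to 6.4.6 add, for Periods 2 to 4, the change from the last value before that period's first dose (V4, V6, V8 or the ESV), summarised by the treatment of that period. Apply the same reference to any new-abnormality counts that are tabulated. Limit this to variables measured at those visits: protocol 11.2.4 and 11.2.8 list blood collection before dosing there, but the analytes are blacked out, and no blood collection is legible at V5, V7 or V9.

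The cost is SAP wording, one derived variable and one more display; no new data are needed for variables already measured at those visits. The added change is noisier and can hide a change already present, which is why both should be shown side by side.
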